5.1. Inclusion Criteria

Each potential participant must satisfy all of the following criteria to be enrolled in the study:

- 1. Male or female (according to their reproductive organs and functions assigned by chromosomal complement).
- 2. 18 to 75 years of age, inclusive.

Type of Participant and Disease Characteristic

- 3. Medically stable on the basis of physical examination, medical history, vital signs, and 12-lead ECG performed at screening. Any abnormalities, must be consistent with the underlying illness in the study population and this determination must be recorded in the participant's source documents and initialed by the investigator.
- 4. Medically stable on the basis of clinical laboratory tests performed at screening. If the results of the serum chemistry panel including liver enzymes, blood coagulation, hematology, or urinalysis are outside the normal reference ranges, the participant may be included only if the investigator judges the abnormalities or deviations from normal to be not clinically significant or to be appropriate and reasonable for the population under study. This determination must be recorded in the participant's source documents and initialed by the investigator.
- 5. Diagnosis of SSc according to ACR and EULAR 2013 criteria.
- 6. Diffuse cutaneous SSc according to the LeRoy criteria ie, skin fibrosis proximal to the elbows and knees in addition to acral fibrosis.
- 7. Disease duration of ≤36 months (defined as time from first non-Raynaud phenomenon manifestation).
- 8. \geq 10 and \leq 22 mRSS units at screening and Week 0.
- 9. FVC \geq 60% of predicted at screening.

- 10. DLCO ≥40% of predicted (hemoglobin-corrected) at screening.
- 11. Participants who meet 1 of the following criteria at screening:
 - a) Increase of ≥ 3 mRSS units, compared with an assessment performed within the previous 2 to 6 months.*
 - b) Involvement of 1 new body area with an increase of ≥2 mRSS units compared with an assessment performed within the previous 2 to 6 months.*
 - c) Involvement of 2 new body areas with increase of ≥ 1 mRSS units compared with the assessment within the previous 2 to 6 months.*

- 12. Criterion modified per Amendment 1
 - 12.1 Have screening laboratory test results within the following parameters, if 1 or more of the laboratory parameters is out of range, a single retest of laboratory values is permitted:

1			
a.	Hemoglobin	≥9 g/dL	SI: ≥90 mmol/L
b.	White blood cells	$\geq 3.0 \times 10^3/\mu L$	SI: ≥3.0 GI/L

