Refer to the Schedule of Activities (Section 1.3) for the timing and frequency of all sample collections.

Study-Specific Materials

The investigator will be provided with the following supplies:

- Investigator Site File (includes protocol and IB)
- IPPM and IPPI
- Instruction for use of prefilled syringe for site staff
- Instruction for use of prefilled syringe for subjects
- Training guide for investigators for use of prefilled syringe
- Subject diary for at home administration / self-administration
- Laboratory manual
- eCRF completion instructions
- Participant recruitment materials (if needed)
- Sample ICF
- PRO questionnaire and PRO completion guidelines
- IWRS manual
- CT image acquisition procedure manual and CT technologist instruction form
- Biopsy manual
- Capillaroscopy manual and quick reference guide
- Pulmonary function test manual

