5.4.2. Secondary Efficacy Endpoints

The secondary efficacy endpoints are:

- Change from baseline in mRSS at Week 52
- The proportion of participants who experience worsening of mRSS at Week 24 and Week 52
- The proportion of participants achieving a score of 0.6 in American College of Rheumatology Combined Response Index in dcSSc (ACR CRISS) at Week 24 and Week 52

- Change from baseline in forced vital capacity (FVC) and percent predicted FVC at Week 24 and Week 52
- Change from baseline in the measured absolute diffusing capacity of the lung for carbon monoxide (DLCO) and the derived percent predicted DLCO at Week 24 and Week 52
- Change from baseline in digital ulcer counts at Week 24 and Week 52
- Change from baseline in Health Assessment Questionnaire-Disability Index (HAQ-DI) score at Week 24 and Week 52

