5.4.2.1. Definition of Endpoints

Worsening of mRSS

An increase from baseline ≥ 5 points and $\geq 20\%$ in mRSS.

American College of Rheumatology Combined Response Index in dcSSc (ACR CRISS)

ACR CRISS is a composite response index for clinical trials in early dcSSc. Application of ACR CRISS algorithm in a randomized clinical trial is a 2-step process.

Step 1: if a patient develops any of the following conditions, they will be assigned a probability of improving equal to 0.0. Investigators will evaluate if the participants have the criterion.

- new scleroderma renal crisis
- decline in percent predicted FVC $\geq 15\%$ relative to baseline confirmed by a second FVC within one month, HRCT to confirm ILD (if previous HRCT did not show ILD) and FVC $< 80\%$ of predicted attributable to systemic sclerosis
- new onset of left ventricular failure (defined as left ventricular ejection fraction $\leq 45\%$) requiring treatment, attributable to systemic sclerosis
- new onset of pulmonary arterial hypertension on right-sided heart catheterization requiring treatment, attributable to systemic sclerosis

Step 2: for the remaining patients, compute the predicted probability of improving for each participant using the following equation (equation to derive predicted probabilities from a logistic regression model):

$$\frac{\exp [-5.54 - 0.81 * \Delta_{MRSS} + 0.21 * \Delta_{FVC\%} - 0.40 * \Delta_{Pt-glob} - 0.44 * \Delta_{MD-glob} - 3.41 * \Delta_{HAQ-DI}]}{1 + \exp [-5.54 - 0.81 * \Delta_{MRSS} + 0.21 * \Delta_{FVC\%} - 0.40 * \Delta_{Pt-glob} - 0.44 * \Delta_{MD-glob} - 3.41 * \Delta_{HAQ-DI}]}$$

where, Δ_{MRSS} indicates the change in mRSS from baseline to follow-up, $\Delta_{FVC\%}$ denotes the change in percent predicted FVC from baseline to follow-up, $\Delta_{Pt-glob}$ indicates the change in patient global assessment, $\Delta_{MD-glob}$ denotes the change in physician global assessment, and Δ_{HAQ-DI} is the change in HAQ-DI. All changes are absolute change.

Participants for which the predicted probability is greater or equal to 0.60 are considered improved while participants for which the predicted probability is below 0.60 are considered non-improved.

Forced Vital Capacity (FVC)

FVC and % predicted FVC are measurements of lung function and will be performed locally.

Diffusing Capacity of the Lung for Carbon Monoxide (DLCO)

DLCO is the measurement of lung function and will be reported locally.

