% predicted DLCO (hemoglobin-corrected) is only collected at screening, while for other visits, it will be derived based on following steps:

- 1) Compute Body Surface Area (BSA) per formula as below:

$$BSA (m^2) = Weight (kg)^{0.425} \times Height (cm)^{0.725} \times 0.007184$$

The Weight of the same visit should be used, if Weight of the visit is missing then the value closest to date of DLCO measurement will be used.

- 2) Compute the predicted DLCO (ml/min/mm Hg) per formula as below:

Male:

$$\text{Predicted DLCO (ml/min/mm Hg)} = 15.5 \times BSA - 0.238 \times \text{age} + 6.8$$

Female:

$$\text{Predicted DLCO (ml/min/mm Hg)} = 15.5 \times BSA - 0.117 \times \text{age} + 0.5$$

- 3) Compute the predicted DLCO (Hgb-corrected) (ml/min/mm Hg) per formula as below:

Male:

$$\text{DLCO (ml/min/mm Hg)} \times ((10.22 + \text{Hgb}) / (1.7 \times \text{Hgb}))$$

Female:

$$\text{DLCO (ml/min/mm Hg)} \times ((9.38 + \text{Hgb}) / (1.7 \times \text{Hgb}))$$

The Hgb (g/dL) of the same visit from central lab will be used.

- 4) Compute the % predicted DLCO (Hgb-corrected) per formula as below:

$$\% \text{ predicted DLCO (Hgb corrected)} = \frac{\text{Predicted DLCO (Hgb corrected) (ml/min/mm Hg)}}{\text{Predicted DLCO (ml/min/mm Hg)}} \times 100$$

Health Assessment Questionnaire -Disability Index (HAQ-DI)

The Stanford HAQ is a brief self-report questionnaire assessing physical function pertaining to activities of daily living across 8 domains: dressing and grooming, arising, eating, walking, hygiene, reach, grip, and activities. The Stanford HAQ translated into Japanese with culturally

appropriate modifications of the arising, eating, and reach category questions will be used in the study. (Matsuda 2003).

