Change from baseline in digital ulcer counts at Week 24	Difference in LSMs of change from baseline in digital ulcer counts at Week 24 between guselkumab vs placebo
Change from baseline in digital ulcer counts at Week 52	Difference in LSMs of change from baseline in digital ulcer counts at Week 52 between guselkumab vs placebo
Change from baseline in HAQ-DI score at Week 24	Difference in LSMs of change from baseline in HAQ-DI score at Week 24 between guselkumab vs placebo
Change from baseline in HAQ-DI score at Week 52	Difference in LSMs of change from baseline in HAQ-DI score at Week 52 between guselkumab vs placebo

Intercurrent events and their corresponding strategies:

The intercurrent events for all key secondary endpoints at Week 24 are the same as those in the primary estimand, as follows:

1. A prohibited change in SSc medication (for details, see [Appendix 11](#))
2. Discontinuation of study intervention due to lack of efficacy or an AE of Systemic Sclerosis

As rescue medication is available for participants after Week 24, an additional intercurrent event is defined for secondary efficacy endpoints at Week 52.

3. Initiation of rescue medication after Week 24

Intercurrent events 1, 2 and 3 are all handled by the **composite strategy** to assume that the occurrence of intercurrent events indicates an unfavorable outcome. For continuous endpoints, the change from baseline will be zero; and for binary endpoints, the participants are considered as not achieving an improvement (ACR CRISS score ≥ 0.6) or experiencing worsening (an increase from baseline ≥ 5 points and $\geq 20\%$ in mRSS).

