 - 3) Change from baseline in average Number of giant capillaries (>50 μ m)/ length of nailfold; average Number of giant capillaries (>50 μ m)/ length of nailfold = sum (Number of giant capillaries (>50 μ m) of each finger) / sum (length of nailfold of each finger)
 - 4) Change from baseline in average total number of abnormal formed capillaries/ length of nailfold; average Total number of abnormal formed capillaries/ length of nailfold = sum (Total number of abnormal formed capillaries of each finger) / sum (length of nailfold of each finger)
 - 5) Change from baseline in average number of nailfold bleeding/ length of nailfold; average Number of nailfold bleeding/ length of nailfold = sum (Number of nailfold bleeding of each finger) / sum (length of nailfold of each finger)
 - 6) Change from baseline in capillary pattern (shift table, based on worst capillary pattern)
 - 7) Change from baseline in average Blood velocity (mm/s)

- Change from baseline in patient global assessment (PGA) at Week 24 and Week 52
- Change from baseline in physician global assessment (PhGA) at Week 24 and Week 52

And LTE efficacy endpoints:

- Change from baseline and Week 52 in mRSS at Week 76 and Week 104
- The proportion of participants who experience worsening of mRSS at Week 76 and Week 104
- The proportion of participants achieving a score of 0.6 in ACR CRISS at Week 76 and Week 104
- Change from baseline in FVC and percent predicted FVC at Week 76 and Week 104
- The proportion of participants who experience worsening of FVC at Week 76 and Week 104
- Change from baseline in the measured absolute DLCO and the derived percent predicted DLCO at Week 76 and Week 104
- Change from baseline in digital ulcer counts at Week 76 and Week 104
- Change from baseline in fibrotic change assessed with HRCT at Week 76 and Week 104 in participants with baseline fibrosis/fibrotic changes, including:
 - 1) Change from baseline in QLF score by whole lung and each lobe at Week 76 and Week 104 in participants with baseline QLF score of whole lung >0.
 - 2) Change from baseline in QILD score by whole lung and each lobe at Week 76 and Week 104 in participants with baseline QILD score of whole lung >0.
- The proportion of participants who experience worsening of fibrotic change assessed with HRCT at Week 76 and Week 104, including:

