As to time to event endpoint, ie, time to disease worsening, it will be summarized by Kaplan-Meier method, with the median, 25th, and 75th percentiles and 95% CI for the quartiles. The comparison between guselkumab and placebo will use a Cox proportional hazards model adjusting for the stratification factors at randomization. An 80% CI for the hazard ratio (HR) will be produced. The

same intercurrent events and handling strategy defined in Section [5.4.2.2](#) will be applied to this endpoint as well, the detailed definition of censoring and event is described as below:

No.	Situation	Date of Event or Censoring	Outcome
1	Disease worsening: an increase from baseline ≥ 5 and $\geq 20\%$ in mRSS or decrease $>10\%$ from baseline in FVC %	First occurrence of disease worsening	Event
2	A prohibited change in SSc medication on or before Week 52	First occurrence of prohibited change	Event
3	Discontinuation of study intervention due to lack of efficacy or an AE of SSc before Week 52	Date of discontinuation of study intervention	Event
4	Initiation of rescue medication after Week 24 and through Week 52	Date of initiation of rescue medication	Event
5	Other	Date of last mRSS or FVC assessment through Week 52	Censored

Note: if participants had more than one items of 1,2,3,4 occurred, the date of first occurrence will be considered as event date.

Unless otherwise specified, LTE efficacy endpoints will only be summarized using descriptive statistics.

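### Percent predicted DLCO appears to take its baseline as collected at screening and all later values from the SAP formula, with no rule putting both on one scale

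*SAP*

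**What the plan says.** Change from baseline in absolute DLCO and in "the derived percent predicted DLCO at Week 24 and Week 52" is a secondary endpoint (SAP 5.4.2). The long-term extension (LTE) list in SAP 5.5 adds "Change from baseline in the measured absolute DLCO and the derived percent predicted DLCO at Week 76 and Week 104".

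On the source of the values, SAP 5.4.2.1 says that percent "predicted DLCO (hemoglobin-corrected) is only collected at screening, while for other visits, it will be derived based on following steps". The steps are:

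1. body surface area from weight and height;
2. predicted DLCO from body surface area, age and sex;
3. hemoglobin correction of the DLCO value, using same-visit central-laboratory hemoglobin;
4. the ratio of step 3 to step 2, times 100.

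The same section says that "DLCO is the measurement of lung function and will be reported locally", and Protocol 8.1.3 has lung function measured locally. The screening value also serves eligibility: "DLCO ≥40% of predicted (hemoglobin-corrected) at screening" (Protocol 5.1). Table 1 of the Schedule of Activities places pulmonary function tests at screening, Weeks 12, 24 and 52, and early termination.

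Neither document names the reference equation or hemoglobin source behind the collected screening value. The SAP does not define baseline for this endpoint, and its Appendix 2 on changes to protocol-planned analyses is marked not applicable.

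**The concern.** With no test at Week 0, the screening value has to be the baseline. SAP 5.4.2.1 limits the derivation to the other visits, so the change score has a collected number on one side and a sponsor-derived number on the other. Percent predicted depends on its denominator: two equations applied to the same lungs on the same day can give different percentages. Any such difference enters the change score as if it were a change in lung function.

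The stake differs by use:

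- **Within-arm change** takes the full gap. This matters most in the LTE, where all participants receive guselkumab and, unless otherwise specified, "LTE efficacy endpoints will only be summarized using descriptive statistics". No randomized comparison is there to cancel a common gap.
- **The randomized difference at Weeks 24 and 52** is protected against a common gap but not against one that varies between sites or participants, which adds noise.
- **The composite strategy** opens a route to bias. After an intercurrent event, "For continuous endpoints, the change from baseline will be zero" (SAP 5.4.2.2). Those participants carry no gap while the others do, so unequal event rates move part of the gap into the arm difference.

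**Working it through.** The plan gives no DLCO figure to reproduce. Only the formulas come from the documents. The gap sizes, patient values, SDs and event rates are assumptions, shown as ranges.

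**1. The SAP steps on one assumed patient.** Woman aged 52, 156 cm, 52 kg, hemoglobin 12.5 g/dL, measured DLCO 12.0 ml/min/mm Hg.
- Body surface area = 52^0.425 × 156^0.725 × 0.007184 = 1.499 m².
- Predicted DLCO = 15.5 × 1.499 − 0.117 × 52 + 0.5 = 17.64.
- Hemoglobin factor = (9.38 + 12.5)/(1.7 × 12.5) = 1.030.
- Percent predicted = 12.0 × 1.030/17.64 × 100 = 70.0.

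If the site's predicted value were r times the SAP's, the recorded baseline would be 70.0/r, and unchanged lungs would show a change of 70.0 × (1 − 1/r):

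| r | Recorded baseline | Artificial change |
|---|---|---|
| 0.90 | 77.8 | −7.8 |
| 0.95 | 73.7 | −3.7 |
| 1.00 | 70.0 | 0.0 |
| 1.05 | 66.7 | +3.3 |
| 1.10 | 63.6 | +6.4 |

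**2. General size.** From here on, the gap is the relative difference between the collected screening percentage and what the SAP steps would give. At 60% predicted, 60 × (0, 0.05, 0.10, 0.15) = 0, 3, 6, 9 points.

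**3. Hemoglobin source alone.** The step 3 factor for women is 1.0480 at 12 g/dL and 1.0127 at 13 g/dL. The ratio is 1.0349, so one reading in place of the other moves 60% by 60 × 0.0349 = 2.1 points.

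**4. Randomized difference, common gap.** If every baseline is multiplied by the same constant k, the model regresses F − kB on treatment and kB, where F is follow-up and B the true baseline. The treatment coefficient is the same as with B, because the baseline term absorbs the rescaling. The MMRM has a baseline-by-visit term, so this holds at each visit. No bias and no real loss of precision arise before the zero-change rule is considered.

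**5. Randomized difference, gap varying between participants.** Take 28 per arm and baseline normal with mean 60 and SD 15, truncated at 40. The truncated mean is 62.7, the variance 163.5, and the mean square 62.7² + 163.5 ≈ 4096. A gap with SD s adds noise variance N = 4096 × s² to the baseline. After adjustment for that noisy baseline, the residual variance rises by A = 163.5 × N/(163.5 + N), and the standard error by the factor √(1 + A/σ²), where σ is the true change SD.
- s = 5%: N = 10.2, A = 9.6.
- s = 10%: N = 41.0, A = 32.8.

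| True change SD | Gap SD 5% | Gap SD 10% |
|---|---|---|
| 6 | 1.13 | 1.38 |
| 8 | 1.07 | 1.23 |
| 10 | 1.05 | 1.15 |

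Simulated trials, with ANCOVA on one follow-up visit as a simplification of the MMRM, agree to within about 0.03.

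**6. Zero-change rule.** Bias = mean gap in points × difference in event rates. With a 10% gap at 60% predicted (6 points), events in 20% versus 10% give 6 × 0.10 = 0.6 points, and 30% versus 10% give 6 × 0.20 = 1.2 points. The direction follows the sign of the gap.

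**The case against.** The strongest reply is that no mixed scale has been shown. Sites receive a "Pulmonary function test manual" (Protocol 8, study-specific materials). It is not among the documents and may prescribe the SAP equation, in which case the artefact is essentially zero. Screening hematology is assigned to the central laboratory, so central hemoglobin exists at that visit, and nothing suggests a 1 g/dL discrepancy. This stands: the finding is that the plan does not tie the two sources together, not that they disagree.

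A second reply is that baseline as the collected value is an inference. The sentence in SAP 5.4.2.1 may only describe which field is on the case report form, and the endpoint name refers to the derived percentage, which could mean derivation at every visit. That reading is possible, but the SAP confines derivation to the other visits. Two programmers could build two different baselines from this text, which is reason enough to settle it.

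A third reply is reach. Only the percent predicted half of one secondary endpoint and its LTE counterpart are affected. Secondary p-values are nominal, the LTE analysis is exploratory, and absolute DLCO reported alongside could expose a discordant shift. All of this is right and limits the weight of the point. The larger precision losses also need a 10% gap SD varying between participants, and the bias needs both a gap and unequal event rates.

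**Conclusion.** The concern holds. As written, the plan subtracts a baseline collected at screening from follow-up values derived by the SAP, and nothing in either document puts them on one scale. Whether an artefact results depends on the sites' equation and hemoglobin source, which the documents do not give. The possible size runs from zero to several points of within-arm change: 3 to 9 points at 60% predicted for gaps of 5% to 15%. For the randomized comparison the usual consequence is some loss of precision; bias of about 0.6 to 1.2 points needs a 10% gap together with event rates differing by 10 to 20 percentage points. The primary endpoint, absolute DLCO, FVC and ACR CRISS are untouched. It should be fixed because the remedy removes the question whatever equation the sites used.

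**What to change.** Before unblinding, add to SAP 5.4.2.1 that percent predicted DLCO (hemoglobin-corrected) at screening is derived by the same steps 1 to 4, from screening measured DLCO, weight, height, age, sex and central-laboratory hemoglobin. State that this derived value is the baseline for the endpoint, including the LTE, for the MMRM covariate and for the baseline characteristics in SAP Table 6. Keep the collected screening value for the eligibility check only, and list it beside the derived one so that any gap is visible.

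The cost is one SAP sentence and one more visit in an existing derivation. Screening pulmonary function tests, height, weight and hematology are already scheduled, so no new data are needed and no study procedure changes.

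### Percent predicted DLCO is divided by a predicted value recomputed from each visit's weight, so this secondary endpoint moves with body weight when haemoglobin-corrected DLCO has not changed

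*SAP*

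**What the plan says.** SAP 5.4.2 lists as secondary endpoints, at Weeks 24 and 52, "Change from baseline in the measured absolute diffusing capacity of the lung for carbon monoxide (DLCO) and the derived percent predicted DLCO".

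SAP 5.4.2.1 explains the percentage. At screening it is a collected value. At all other visits it is derived in four steps:

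1. Body surface area (BSA) from weight and height. On weight: "The Weight of the same visit should be used", with the value nearest in date to the DLCO measurement as the fallback.
2. Predicted DLCO from BSA, age and sex.
3. A haemoglobin correction of the measured DLCO. On its input: "The Hgb (g/dL) of the same visit from central lab will be used".
4. The step 3 value divided by the step 2 value, times 100.

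Protocol 1.3 (Table 1) schedules weight at the same main-study visits as pulmonary function: screening, Weeks 12, 24 and 52, and early termination. Height is taken at screening only. There is no Week 0 pulmonary function test. Protocol 8.1.3 attaches the haemoglobin correction to percent predicted DLCO and not to absolute DLCO. Neither document fixes the weight at one visit or plans a sensitivity analysis on this derivation.

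**The concern.** A change from baseline in percent predicted DLCO is meant to describe the lung. Under the SAP derivation it has two moving parts: corrected DLCO in the numerator, and a body-size reference that is reset at each derived visit in the denominator. Weight loss with unchanged corrected DLCO reads as improvement, and weight gain reads as worsening.

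At stake is the precision of a secondary endpoint in a trial of 28 participants per arm, and its validity if weight change differs between arms. SAP 5.1.1 says the 80% and 95% confidence intervals for secondary endpoints serve as reference for the internal go/no-go decision, so the estimate will be used.

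**Working it through.** The documents state no numerical DLCO result, so there is no figure to reproduce. The check applies the SAP equations to assumed participants. Heights, weights, ages, haemoglobin values and the 70% starting point are assumptions, because neither document gives their distributions.

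**Formulas (SAP 5.4.2.1)**
- BSA = W^0.425 × H^0.725 × 0.007184
- Predicted DLCO, women: 15.5 × BSA − 0.117 × age + 0.5
- Predicted DLCO, men: 15.5 × BSA − 0.238 × age + 6.8
- Haemoglobin factor, women: (9.38 + Hgb)/(1.7 × Hgb); men: (10.22 + Hgb)/(1.7 × Hgb)

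**Weight and percent predicted.** Corrected DLCO and age are held fixed, and the starting value is 70% by the same equation. The new percentage is 70 × (predicted at old weight)/(predicted at new weight).

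Woman, 156 cm, 50 years:

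| Weight | BSA | Predicted DLCO | Percent predicted |
|---|---|---|---|
| 52 kg | 1.499 | 17.88 | 70.0 |
| 51 kg | 1.486 | 17.69 | 70.8 |
| 49 kg | 1.461 | 17.30 | 72.3 |
| 47 kg | 1.436 | 16.90 | 74.0 |

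Man, 168 cm, 50 years:

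| Weight | BSA | Predicted DLCO | Percent predicted |
|---|---|---|---|
| 65 kg | 1.739 | 21.85 | 70.0 |
| 62 kg | 1.704 | 21.31 | 71.8 |
| 60 kg | 1.681 | 20.95 | 73.0 |

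Five further profiles (three women, two men, 45 to 75 kg, 35 to 70 years), also starting at 70%, give:
- 5% weight loss: +1.7 to +2.5 points
- 10% weight loss: +3.6 to +5.2 points
- 5% weight gain: −1.6 to −2.2 points

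**Between arms.** The relation is close to linear over a few kilograms, so an arm difference in mean weight change carries over at about the per-kilogram rate. For the 52 kg woman, 1 kg gives 70 × 17.88/17.69 − 70, about 0.8 points.

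**Baseline.** With no Week 0 test, the pre-treatment percentage is the collected screening value, whose equation is not stated. If the screening reference differed from the SAP equation by an assumed 5% or 10%, a 70% value would shift by 70 × 0.05 = 3.5 or 70 × 0.10 = 7 points with nothing changed in the participant. Fixing the weight alone would leave this in the change from baseline.

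**Haemoglobin and absolute DLCO.** With corrected DLCO held fixed, measured DLCO is corrected DLCO divided by the factor.
- Woman, 12 to 11 g/dL: the factor goes from 1.0480 to 1.0898, so measured DLCO falls by 1 − 1.0480/1.0898 = 3.8%.
- Man, 13.5 to 12.5 g/dL: the factor goes from 1.0336 to 1.0692, a fall of 3.3%.

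Haemoglobin does not move the percentage, because step 3 removes it. Weight does not enter absolute DLCO. Each endpoint carries one of the two influences, not both.

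**The case against.** The strongest reply is that current body size is a coherent reference: the participant is compared with someone of the same present size. In a randomized, blinded comparison the weight effect is noise unless weight change differs by arm. Weight change is summarised under SAP 5.7.3.2, by intervention group under SAP 5.7, so an imbalance could be seen. Absolute DLCO is free of weight and gives a cross-check. The endpoint is secondary with nominal p-values (SAP 5.4.1), the proof-of-concept test rests on mRSS, and DLCO is not a component of ACR CRISS. A loss of 3 to 5 kg from 52 kg is 6 to 10% of body weight, which is large for an average.

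Most of this stands, and it limits the weight of the point. It does not remove it. Seeing an imbalance in a safety table does not adjust the DLCO estimate, and the noise is avoidable.

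Three stronger readings are tempting and are not supported:
- A reader might infer that leaving absolute DLCO uncorrected for haemoglobin is an error. Both documents name that endpoint as the measured value, so it is a pre-specified choice. Measured uptake does change with haemoglobin.
- A reader might infer that the estimated treatment effect is biased. That needs a difference between arms in weight change, and the documents give no data on one.
- A reader might infer that weight loss from worsening disease would hide lung deterioration. Neither document links weight loss to SSc progression. Weight loss appears only among the tuberculosis symptom questions in Protocol 8.2.9.2.

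**Conclusion.** The point holds for percent predicted DLCO. The denominator follows weight at each post-screening visit, so the endpoint shifts by about 1.8 to 2.3 points for a 3 kg loss at a 70% start, and by roughly 0.8 points per kilogram of arm difference in a 52 kg woman. These sizes rest on assumed participants and on baseline being calculated with the SAP equation, which the SAP does not currently do. The consequence is added variability in a secondary endpoint, with bias only if weight change differs by arm. The primary endpoint and sample size are untouched. A change is worth making before unblinding because it is cheap. The haemoglobin observation justifies an optional supplementary analysis and no more.

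**What to change.** In SAP 5.4.2.1:

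- Compute predicted DLCO once per participant from screening weight, height and age with the SAP equation, and use it as the denominator at all visits.
- Re-derive the screening (baseline) percentage from screening DLCO and screening haemoglobin with the same equation, in place of the collected value for the change-from-baseline analysis. Without this step the change still mixes two methods.
- Keep the current-weight derivation as a sensitivity analysis if wanted.
- Optionally, report change in the haemoglobin-corrected absolute DLCO from step 3 with the same MMRM, as supplementary to measured absolute DLCO, which stays the pre-specified endpoint.
- Relabel step 3, which calls its result a predicted DLCO although it corrects the measured one.

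The cost is SAP wording, one derivation change and one extra table for each optional analysis. No new data are needed: weight, height, haematology and pulmonary function are all taken at screening. The downside is that later percentages are relative to baseline body size and age. Freezing age also removes a small drift, about 0.5 points per year in the example woman and 0.8 in the man at a 70% start.
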